At the Center for Cell and Gene Therapy, Baylor College of Medicine, Houston, TX, [name] and [name] were Principal Investigators (PIs) on a clinical study in which subjects with CD19+ B-cell lymphomas were infused simultaneously with two autologous T-cell products [26]. Each product contained cells expressing the identical CAR exodomain specific for the CD19 antigen (CD19-specific scFv) present on many B-cell derived malignancies. In one product the CAR was coupled to the ζ endodomain (first generation) while in the second product the CAR was coupled to the CD28 and ζ endodomains (second generation). With this study design, each subject acted as "a self-control", allowing us to directly discover, even in a small study with heterogeneous subjects, the consequences of incorporating a co-stimulatory endodomain on the fate of engineered T cells *in vivo*. Six subjects with B-cell lymphomas relapsed after multiple cycles of therapy using conventional treatments were enrolled into the study. For each subject, two T-cell products expressing either CAR.CD19 ζ (first generation) or CAR.CD19-28 ζ (second

Page 40 of 154

generation) were generated. Both cell products were similar by functional and phenotypic analyses. Two subjects for each dose level (2x10⁷, 1x10⁸ and 2x10⁸ cells/m² dose level 1, 2 and 3, respectively) were infused with both sets of CAR.CD19 modified T cells. Infusions were well tolerated without any immediate side effects. Expansion and persistence of CAR-T cells in vivo were assessed in the peripheral blood by quantitative PCR (Q-PCR) assays specific for CAR.19ζ and CAR.19-28 ζ transgenes, respectively. Molecular signals for CAR.19-28 ζ^+ T cells increased from 3 hours after infusion to 1-2 weeks post infusion (representing a 2 to 59 fold expansion). Molecular signals then declined by 6 weeks follow up and did not further expand in vivo. By contrast, molecular signals derived from CAR.19 ζ^+ T cells that were detected 3 hours after infusion did not show significant expansion thereafter (from 0 to 1 fold expansion), and had become almost undetectable by 6 weeks. These data indicate that the infusion of second generation CD19- specific CAR-T cells is safe at the doses so far tested and that CD28 does indeed provide a co-stimulatory signal in vivo in subjects with B-cell lymphoma [26].

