1.6 Study Design and Rationale

ASCT may be the only curative option for subjects with refractory/relapsed hematological malignancies. Despite ASCT, disease recurrence remains the major cause of treatment failure. Hence development of non-toxic consolidation treatments after transplant remains a highly desirable objective, and the adoptive transfer of CTLs is one promising approach [64-67].

In this Phase I multicenter study, peripheral blood will be collected for production of ATLCAR.CD30 cells in subjects with CD30⁺ lymphoma at high risk of relapse post-transplant, and scheduled to undergo ASCT. Three dose levels will be evaluated to identify the MTD in this population: Level $1 = 2 \times 10^7 \text{ CAR}^+ \text{ T cells/m}^2$; Level $2 = 1 \times 10^8/\text{m}^2$; Level $3 = 2 \times 10^8/\text{m}^2$. The total number of cells infused will be calculated on the number of CAR-T cells as requested by the FDA. Similar to the prior phase I

LCCC1524-ATL
Administration of T lymphocytes Expressing the CD30 Chimeric Antigen Receptor (CAR)
for Prevention of Relapse of CD30+ Lymphomas after High Dose Therapy and Autologous
Stem Transplantation (ATLAS)
ATLCAR.CD30

summarized in section 1.5.5, we will monitor the persistence of these infused cells in the peripheral blood of the subjects and whenever lymph nodes are biopsied as per routine clinical care during the first year after treatment at the tumor site by measuring the level of the transgene by both phenotypic and molecular analyses. Currently, we can regularly detect a single transduced cell in 50,000 peripheral blood mononuclear cells by real-time PCR amplification. Moreover, because gene persistence and expression may not correlate with antitumor effector function, we will also determine the functionality of the peripheral blood T cells *ex vivo*.

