11.3.3 Analysis of Expansion and Persistence of Transduced T Cells

The frequency of T cells transduced with the vector (T cells expressing will be summarized at pre and post-infusion time points using mean \pm SD, medians and ranges to evaluate their expansion and persistence. Changes in each of these T cells from pre-infusion to each time point of post-infusion will be assessed and compared using paired t-tests, or when appropriate, the Wilcoxon signed ranks test. Paired comparisons of these T cells within a subject at each time point will also be performed. These analyses will be performed in the overall subject group.

Plots of growth curves will be generated to graphically illustrate patterns of T-cell expansion. Plots will be generated to depict patterns of survival and expansion of T cells for each of the two vectors. Longitudinal modeling techniques such as the random coefficient mixed model will be employed to model each of the repeatedly-measured T cells. These models account for variation in individual-level intercepts and slopes over the follow-up time. Thus, we will be able to model proliferation of T cells over time and estimate the magnitude of expansion or decline of T cells. We will include dose level as an independent variable in the model to account for different doses received by subjects.

Alternative strategies to analyze these outcomes include calculation of area under the curve over time for T cell frequencies or piecewise longitudinal models based on apparent trends from plots of growth curves. Despite the small subject numbers, a datadense study will be generated due to the repeat measurements on proliferation, immune function, etc. on each subject. The modeling strategies proposed here are amenable to these types of data but will however be considered exploratory and interpreted with caution due to limited study power.

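### Section 11.3.3 sets out to evaluate expansion, but its named paired test is against pre-infusion and so tests presence; the scheduled 3-4 h sample should be the reference for expansion

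*Combined protocol and SAP*

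**What the plan says.** Section 11.3.3 summarises the frequency of transduced T cells before and after infusion by mean, SD, "medians and ranges to evaluate their expansion and persistence". The test is then specified: "Changes in each of these T cells from pre-infusion to each time point of post-infusion will be assessed and compared using paired t-tests", with the signed-rank test as the alternative. The section adds: "Paired comparisons of these T cells within a subject at each time point will also be performed". It does not say what is compared with what. It also plans growth-curve plots, a random-coefficient mixed model with dose level as a covariate and, as alternatives, area under the curve or "piecewise longitudinal models based on apparent trends from plots of growth curves". The modelling is labelled exploratory. No significance level, measurement scale, time origin for expansion or value for undetectable results is given.

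Other sections supply the context:

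- There is a single infusion (4.1.3 and 6.1).
- qPCR samples are scheduled before infusion, at 3-4 h, at weeks 1 to 6 and at months 3 to 12 (7.2.3 and 7.4).
- Persistence is a secondary endpoint (3.2.3). Expansion appears in the heading and aim of 11.3.3 and is used again in 11.3.5.
- In the earlier two-product study described in 1.5.1, signals from the second-generation product "increased from 3 hours after infusion to 1-2 weeks post infusion (representing a 2 to 59 fold expansion"). Those from the first-generation product, also followed from 3 hours, "did not show significant expansion thereafter (from 0 to 1 fold expansion").
- On assay sensitivity, 1.6 states: "we can regularly detect a single transduced cell in 50,000 peripheral blood mononuclear cells by real-time PCR amplification".

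**The concern.** Expansion means that the level in blood rises after the cells have been given. A sample taken before the only infusion contains none of the product, so any detectable later value is an increase over it, whether the level has since risen, held steady or fallen. A small p-value for change from pre-infusion could therefore be reported as expansion when cells had only stayed detectable.

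The protocol's own background draws the line differently. Section 1.5.1 tells an expanding product from a non-expanding one by the change from 3 hours. This trial collects the equivalent sample, but 11.3.3 does not name it as a reference. The paired comparisons within a subject do not fill the gap. With no comparator named, they read as comparisons within a visit. The neighbouring sentence, "Plots will be generated to depict patterns of survival and expansion of T cells for each of the two vectors", does not fit the single CAR.CD30 vector of 8.1. At stake is how a secondary or exploratory result is read, and the expansion measure carried into 11.3.5.

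**Working it through.** The plan gives no power, alpha or effect size for this analysis, so there is no stated figure to reproduce.

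**Inputs from the documents.** 12 to 18 subjects (11.2). Sensitivity of 1 in 50,000, or 0.002% (1.6). Fold changes of 1, 2 and 59 (1.5.1).

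**Assumptions.** Pre-infusion value of 0. Two-sided 0.05. Log-normal 3-4 h levels with median 5, 20 or 100 times the limit of detection (LOD), that is 0.01%, 0.04% or 0.2%. Log-SDs of 1 or 1.5, both between subjects and between visits. Ten-fold changes, because √(2 × 59) = 10.9 is the geometric middle of 2 and 59.

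**Signed-rank test, exact.** With pre-infusion at 0 and undetectable subjects dropped as zero differences, all k remaining differences are positive. One of 2^k sign patterns is that extreme in each direction, so p = 2/2^k:

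- k = 5: 0.0625
- k = 6: 0.031
- k = 8: 0.0078
- k = 12: 0.00049
- k = 18: 0.0000076

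Only the number detectable enters the formula. The test is significant from six detectable subjects upward.

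**Raw-scale t-test.** t = mean/(SD/√n). Multiplying every value by a common factor leaves t unchanged. One simulated data set of 12, multiplied by 10, 1 and 0.1, gave p = 5.1e-05 each time.

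**Simulation.** 3,000 trials per setting; ranges run over n = 12 or 18 and the SDs. Results below LOD are 0 against pre-infusion, and LOD/2 on the log scale. The table gives the share of trials with a significant increase over pre-infusion:

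| Later visit relative to 3-4 h | Signed-rank, 20-100 × LOD | Raw t, 20-100 × LOD | Signed-rank, 5 × LOD | Raw t, 5 × LOD |
|---|---|---|---|---|
| Ten-fold fall | 89-100% | 30-87% | 13-72% | 16-51% |
| No change | 100% | 35-86% | 99-100% | 34-84% |
| Ten-fold rise | 100% | 34-86% | 100% | 36-85% |

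For fold changes of 1, 2 and 59, the signed-rank test rejects in 99-100% at every level.

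**Same data, reference changed to 3-4 h, all levels:**

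| Later visit relative to 3-4 h | Log-scale t-test | Raw-scale t-test |
|---|---|---|
| Ten-fold fall, found as a fall | 97-100% | 48-98% |
| No change | 2-5% false rises, 1-3% false falls | not tabulated |
| Two-fold rise, found as a rise | 30-81% | 10-58% |
| Ten-fold rise, found as a rise | over 99% | 31-84% |

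**Mixed model, only if the pre-infusion value enters a straight line on log10.** With balanced visits, the fixed slope is the least-squares slope of the mean profile. Days used were 0, 0.15, 7, 14, 28 and 42, with pre-infusion set between LOD/2 and LOD. A true ten-fold decline to week 6 is then estimated as:

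- 3.5- to 4.8-fold at 5 × LOD
- 1.9- to 2.6-fold at 20 × LOD
- between a 1.1-fold rise and a 1.25-fold decline at 100 × LOD

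With visits to month 12 and the decline spread over that time, the estimates are 5.7- to 6.8-fold, 4.1- to 4.9-fold and 2.8- to 3.3-fold.

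**The case against.** **The p-values are not always alike.** A reader might infer that the test returns the same p-value whatever happens after infusion. That holds exactly for the signed-rank test only when the same number stay detectable, and for the raw t-test only under a common fold change. At 20 × LOD with n = 12, about 8 subjects remain detectable after a ten-fold fall, so p is about 0.008 against 0.0005 when all 12 do (0.0078/0.00049 = 16 times larger). At 5 × LOD the signed-rank test does separate a fall. After a 100-fold fall it rejects in at most about 5% of trials at 5-20 × LOD, though in 60-95% at 100 × LOD (no added visit noise). So a product that becomes almost undetectable, as 1.5.1 describes by week 6 for the first-generation product, could be told apart at the lower levels. This stands.

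**The section has other tools.** A reader might infer that 11.3.3 cannot show expansion at all. It can: visit summaries, curves and the exploratory models all carry direction, and p-values would be read beside them. What remains is that none of these names a starting time for expansion.

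**The gain is not all from the reference time.** The two columns of the second table show that much of the power comes from the log scale, which 11.3.3 neither requires nor rules out.

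**The mixed-model bias is conditional.** The section does not say that pre-infusion enters the model, and it offers piecewise fits. The documents do not support a claim that the planned model is biased.

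**Some text is not visible.** The exploratory objectives and endpoints (2.3 and 3.3) are blank, and 11.3.3 has a gap where the counted cells are described. Expansion might be defined in the former. The reference time of the paired test, however, is stated in full.

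**Conclusion.** The point holds in this form: the named paired test measures presence, not expansion. When most subjects stay detectable (20-100 × LOD under the assumed levels), it usually gives the same decision at two-sided 0.05 for a rise, no change or a ten-fold fall. For the signed-rank test the rates are 100%, 100% and 89-100%. At low levels or after larger falls it does discriminate.

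The exact result needs only a pre-infusion value of zero, which the documents do not state but which follows from a single later infusion. The percentages also rest on assumed levels, SDs and alpha. As a test of persistence the contrast is sound. No dose, stopping rule or safety analysis depends on it.

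**What to change.** In 11.3.3:

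1. For expansion, analyse the within-subject log change from the 3-4 h sample to each later visit, and report the ratio of peak to 3-4 h level with a confidence interval.
2. State the value used below detection, for example LOD/2, with LOD as a sensitivity check.
3. Start the mixed, area-under-the-curve and piecewise analyses at 3-4 h.
4. Keep pre-infusion as the negative control, and report persistence as the proportion detectable at each visit.
5. Name the comparator for the within-subject paired comparisons.

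The cost is a few lines of text, a small extra analysis and a simple imputation; the samples are already scheduled. Two limits remain. Power for a two-fold rise is only 30-81%. The log-scale t-test is also sensitive to the imputed value if many subjects become undetectable. With a quarter undetectable regardless of level and a floor at 1/100 of the median 3-4 h level, it found a ten-fold rise in only 13-17% of trials, against 75-97% for a signed-rank test from 3-4 h. That is a reason to keep the sensitivity check and the signed-rank option that 11.3.3 already allows.

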11.3.4 Analysis of Progression Free Survival

PFS is defined in section 3.2.1. We will estimate PFS using the Kaplan-Meier method.

Page 101 of 154

11.3.5 Analysis of Integration Location and CAR T cell Behavior

Differential CAR-T cell behavioral analysis will be described by comparing CAR.CD30 integration location with CAR-T cell behaviors such as expansion, persistence and trafficking. Logistic regression will be used with loss of response to the experimental therapy as an outcome to assess potential causes for loss of responses. Additionally, we will assess the correlations between CAR T cell behavior and the integration locations of CAR.CD30.

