1.0 INTRODUCTION AND RATIONALE

1.1 Study Synopsis

This open label, single-arm multicenter study is designed to identify the maximum tolerated dose (MTD) within 3 dose levels of autologous T lymphocyte chimeric antigen receptor cells (ATLCAR) targeted against the CD30 antigen (ATLCAR.CD30). This phase I design uses the continual reassessment method (CRM), a Bayesian adaptive method for estimating the MTD. Subjects with CD30+ lymphoma at high risk of relapse will receive one infusion of ATLCAR.CD30 after undergoing an autologous stem cell transplant (ASCT) for treatment of recurrent disease. The study will enroll up to a maximum of 18 subjects. Secondary endpoints include evaluation of persistence of ATLCAR.CD30 cells in vivo, and progression free survival (PFS). Study participants may be given the option to complete patient reported outcomes (PRO) questionnaires during the study.

LCCC1524-ATL builds on the prior clinical trial experience of UNC investigators Drs. [name] and [name] during their time at Baylor College of Medicine in Houston Texas. Reference in this protocol to their previous related trial experience is referring to work done at Baylor College of Medicine Cell and Gene Therapy Program (BCM-CAGT).

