6.0 STUDY CONDUCT

6.1 **Duration of Therapy**

Therapy in LCCC1524-ATL involves just one infusion of ATLCAR.CD30 cells. Treatment with one infusion will be administered unless:

- Subject decides to withdraw from study treatment, OR
- General or specific changes in the subject's condition render the subject unacceptable for further treatment in the judgment of the investigator.

6.2 **Duration of Follow-Up**

Subjects will be followed for up to 15 years or until death, whichever occurs first. Subjects removed from study for unacceptable adverse events will be followed until resolution or stabilization of the adverse event.

Subjects who experience disease progression and start alternate therapy after receiving a cell infusion(s) will still be required to complete abbreviated follow up procedures outlined in APPENDIX IV - Abbreviated Follow Up Required After Initiating Alternative Therapy (section 18.4).

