7.8 Assessment of Efficacy

To assess disease status, imaging will be performed at baseline (within 60 days prior to ASCT) and at 6-8 weeks, 6 months, 12 months, 18 months and 24 months (or until documented disease progression) following the infusion. The choice of imaging will depend on what studies have been most informative in following the subject's disease (i.e., PET, CT scans, MRI, nuclear imaging). If imaging studies are performed at other times after treatment on this study; that data will be collected and information gained will be used for this study.

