11.2 Sample Size

The trial will continue until a minimum of 12 subjects is treated. Six additional subjects might be accrued to obtain more data. Assignment of these subjects will be guided by the CRM. However, a lower dose can be chosen for assignment. Depending on subject availability, a maximum of 18 subjects will be accrued into this Phase I trial. The final MTD will be the dose with estimated probability of the DLT closest to the target toxicity rate of 10%. All subjects, adult and pediatric, will be included in MTD estimation. We therefore expect to enroll between 12-18 subjects into this trial.

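### Section 11.3.5 models loss of response by ordinary logistic regression with no time window or censoring, so follow-up length can pass for an effect, and at 12–18 subjects the odds ratio can be infinite

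*Combined protocol and SAP*

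**What the plan says.** Section 11.3.5 gives one sentence on this model: "Logistic regression will be used with loss of response to the experimental therapy as an outcome", with the aim of finding what might explain that loss. Its other two sentences compare and correlate integration location with T-cell behaviour. The visible text does not say which subjects enter the model, by what date loss is counted, how subjects still in response at last contact are handled, or which predictors are used.

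Other sections bear on it:

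- **Follow-up.** Section 6.2: "Subjects will be followed for up to 15 years or until death, whichever occurs first". Section 6.4 provides for withdrawal.
- **Disease assessment.** Section 7.8 schedules imaging at 6–8 weeks and then at "6 months, 12 months, 18 months and 24 months (or until documented disease progression) following the infusion". It also uses unscheduled scans: "If imaging studies are performed at other times after treatment on this study". Section 7.1.1 has different imaging rules for cutaneous lymphomas, and the abbreviated schedule in Appendix IV lists no imaging.
- **Sample size.** Section 11.2: "The trial will continue until a minimum of 12 subjects is treated. Six additional subjects might be accrued to obtain more data", and "a maximum of 18 subjects will be accrued into this Phase I trial". Section 1.1 agrees; the Study Summary says 40 subjects.
- **Related endpoint.** Section 11.3.4 estimates PFS by Kaplan-Meier.
- **Candidate causes.** Section 7.5.7 names only loss of CD30 expression, read from biopsy or autopsy tissue taken at any time after treatment, and leaves the list open.
- **Definition.** In the visible text, loss of response is defined only in the response tables for cutaneous lymphomas, mycosis fungoides and Sézary syndrome.

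**The concern.** Whether a subject has lost response depends on how long that subject has been watched. A yes/no model without a window compares subjects seen for different lengths of time as if they were equivalent. The neighbouring PFS analysis handles the same feature by censoring; this one does not.

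Follow-up length is not random here. Section 11.1 starts at the lowest dose and escalates, so at any common data cut-off the lower-dose subjects tend to have been observed longest. They would show more losses for that reason alone, and higher doses would look protective.

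The second difficulty is size. With 12–18 subjects, a two-by-two table of loss against a binary predictor may have an empty cell. Ordinary logistic regression then has no finite estimate and its Wald interval is meaningless.

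What is at stake is a correlative result: a follow-up artefact could be reported as a cause of treatment failure.

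**Working it through.** **Sample size.** 12 + 6 = 18, which reproduces the maximum in sections 1.1 and 11.2. The 40 in the Study Summary does not follow from those figures. 18 is also an upper limit for this model, because only subjects with a response can lose it.

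**Follow-up artefact.** The plan gives no rate of loss. For scale only, I take the two median PFS values that section 1.4 cites from the post-transplant brentuximab vedotin trial, 24.1 and 42.9 months. I assume exponential loss with the same hazard in both groups, so the true effect is nil.

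Hazard λ = ln 2 / median. Loss by time t is p(t) = 1 − exp(−λt). The odds ratio for follow-up t₁ against t₂ is [p(t₁)/(1 − p(t₁))] / [p(t₂)/(1 − p(t₂))].

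| Median (months) | λ | p(24) | p(12) | p(6) | OR, 24 v 12 | OR, 24 v 6 |
|---|---|---|---|---|---|---|
| 24.1 | 0.0288 | 0.499 | 0.292 | 0.158 | 2.41 | 5.28 |
| 42.9 | 0.0162 | 0.321 | 0.176 | 0.092 | 2.21 | 4.65 |

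For example, in the first row 0.994 / 0.412 = 2.41. If every subject is assessed over the same 24 months, the odds ratio is 1.0. These figures take a predictor that splits subjects exactly by follow-up length; partial alignment gives a smaller distortion.

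Expected losses by 24 months if all are at risk: 18 × 0.321 = 5.8 to 18 × 0.499 = 9.0, or 3.9 to 6.0 with 12 subjects.

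**Infinite estimates.** Take one binary predictor with prevalence q, loss probability p in both groups and n subjects. The estimate is finite only if both groups contain both outcomes. Summing over the number k with the predictor:

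P(infinite or undefined) = 1 − Σₖ C(n,k) qᵏ(1−q)ⁿ⁻ᵏ · f(k) · f(n−k), where f(m) = 1 − pᵐ − (1−p)ᵐ and f(0) = 0.

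| n | loss p | q = 20% | q = 30% | q = 50% |
|---|---|---|---|---|
| 12 | 20% | 72% | 59% | 50% |
| 12 | 33% | 57% | 37% | 24% |
| 12 | 50% | 50% | 28% | 13% |
| 18 | 20% | 53% | 38% | 28% |
| 18 | 33% | 35% | 18% | 8% |
| 18 | 50% | 28% | 11% | 2% |

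So the range over 20–50% loss and 20–50% prevalence is 2–53% at N = 18 and 13–72% at N = 12. For one continuous predictor at N = 18, simulation gives only 0–3%.

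**Does a change to Cox alone help?** Simulated at N = 18 with no effect, 24-month follow-up and 25% prevalence, ordinary Cox regression has an infinite estimate in 9% of trials (median 24.1) or 23% (median 42.9), against 18% and 26% for logistic regression. With 12-month follow-up and median 42.9 both are at 50%. Small numbers cause this, so the cure is penalisation; modelling time is what cures the follow-up artefact.

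**The case against.** There are several fair points on the other side.

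- **Separation is conditional.** A reader might infer that the model will usually fail. The documents do not support that: they give neither predictors nor a loss rate. With a balanced predictor at N = 18 the chance is 8% at 33% loss and 2% at 50%. If 40 were the true size, it would be 0.3–4.5% at 30% loss and 25–50% prevalence. Only the statement that estimates can be infinite stands.
- **Bias needs a link.** A reader might infer that every estimate is distorted. Only predictors correlated with follow-up length are, and the documents report no such correlation. Dose level is a plausible candidate because of sequential dosing. Manufacturing batch is not, because each product is autologous and made for one subject.
- **A common window is attainable.** Follow-up is planned well beyond the 24-month scan, so a fixed-window logistic model could be sound. That is right, but section 11.3.5 sets no window.
- **A Cox model does not suit the one cause that is named.** Loss of CD30 may be known only from tissue taken at relapse or autopsy, so it cannot serve as a baseline predictor. This stands and limits the remedy.
- **Redaction.** The exploratory objectives and endpoints are not visible in the public copy, and a definition, time frame or exploratory label may lie there. That may settle the labelling. It does not alter the method named in section 11.3.5.

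**Conclusion.** The concern holds in limited form. As written, section 11.3.5 applies ordinary logistic regression to an outcome that accrues over unequal follow-up, with no window or censoring. A predictor aligned with follow-up can then show a spurious odds ratio of roughly 2.2–2.4 (24 v 12 months) or 4.7–5.3 (24 v 6 months). This rests on exponential loss, equal hazards and medians borrowed from another trial. The risk of infinite estimates is real at 12–18 subjects but depends on the setting, and it would arise under ordinary Cox regression too.

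A reader might infer that the trial's main conclusion is at risk. It is not: this is a correlative analysis and does not enter MTD estimation. The importance is low, but a better method is available from data already collected. The caution about exploratory status in section 11.3.3 refers to the T-cell models there and does not visibly extend to section 11.3.5.

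**What to change.** Replace the logistic regression sentence in section 11.3.5 with the following.

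1. Define loss of response for all disease types and restrict the analysis to subjects at risk of losing it.
2. For predictors known at or soon after infusion (dose, integration features, early expansion), fit a Firth-penalised Cox model of time from infusion to loss of response. Censor at the last disease assessment and treat death without relapse as a competing event. Enter one predictor at a time and report profile-penalised-likelihood intervals.
3. An acceptable alternative is a Firth logistic model of loss by the 24-month scan, in subjects followed to that point or with earlier loss. Report how many are excluded for shorter follow-up, since dropping them raises the apparent loss rate.
4. Report causes seen only in tissue taken at or after relapse, such as CD30 loss, descriptively.
5. Apply the exploratory caution of section 11.3.3 here, and reconcile 18 with 40 subjects.

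The cost is a short paragraph, a little more analysis work and wider intervals. No new data are needed: the infusion, relapse, death and assessment dates are already required for PFS and overall survival.
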